#### ***4.3.2 Handling of values below (or above) a threshold***

Values below (above) the detection limit will be imputed by the value of the detection limit itself, unless indicated otherwise. Listings will always present the original value. Example: if the database contains values like "<0.04", then for the descriptive statistics the value of the detection limit (0.04) shall be used. A value like ">1000" will be imputed by "1000".

Individual pharmacokinetic concentrations below the limit of detection or below the quantification limit (BQL) will be reported as BQL. To compute descriptive statistics (i.e. mean (or median or geommean), SD, CV%, minimum and maximum), all BQL values will be treated as missing. When the total number of BQL values exceeds 1/3 of the total number of values at that time point, descriptive statistics will not be computed. Descriptive statistics not calculated for the above reasons will be reported as not calculated (NC).

For handling of titer values from immunogenicity analysis, see section 9.

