^J AEs will be recorded from the time the informed consent form is signed through the Follow-up Visit. The Investigator must follow-up on all SAEs and AEs until the events have subsided, returned to baseline, or the subject's condition has stabilized in cases of permanent impairment. **In case of acute or delayed severe/serious hypersensitivity reactions, an additional serum sample should be collected as soon as possible after the start of the event (blood volume: 5 mL).**

^K PK and immunogenicity samples will be taken predose.

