3.3.6. TREATMENT COMPLIANCE

To ensure treatment compliance, study drug dosing will be supervised by the Investigator or his/her designee, except when study drug is to be self-administered.

The exact times of study drug dosing at the clinical site will be recorded in the (e)CRF. Compliance will be further confirmed by bioanalytical assessment of ALX-0061 in serum samples. Treatments that are administered outside of the scheduled windows, as well as missed visits/administrations, will be recorded in the (e)CRF.

Each subject will be provided with a study drug injection card to collect the date and time of each study drug administration. This information will be recorded on the card by the subject for all study drug doses administered away from clinic.

The subject must bring his/her injection card to all study visits. At each visit, the site will review the card, record the new information in the (e)CRF, and return the card to the subject. Subjects will be instructed to return the completed card at their final visit.

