### **4.3 General Methods**

#### **4.3.1 *Calculation of descriptive statistics***

Continuous variables will be summarized using descriptive statistics including the number of non-missing observations (n), the arithmetic mean, the standard deviation (SD) for general characteristics and for PK summaries or standard error (SE) for efficacy, safety and immunogenicity, the median, minimum and maximum.

Descriptive statistics of efficacy will additionally include a 95% confidence interval (CI) of the mean, calculated based on the large sample normal approximation. For changes from

baseline of efficacy parameters, the least squares (LS) mean and 95% CI derived from an ANCOVA model with treatment group as factor and baseline as covariate will be shown.

Descriptive statistics of PK concentrations will additionally include 5% and 95% percentiles, coefficient of variation (CV)% of arithmetic mean, geometric mean and geometric SD.

Descriptive statistics of continuous variables will be presented when  $n \geq 2$ . When  $n=1$ , only sample size (n) and mean are shown.

Categorical variables will be summarized using frequency counts and percentages. For efficacy, a Wilson score 95% CI on the percentage in each treatment group will also be shown. When count data are presented, the percentage will be suppressed when the count is zero. Missing values will not be included in the denominator count when computing percentages. For demographics and baseline disease characteristics a 'missing' row will be included to indicate the number of missing values, without percentages.

For the graphs showing mean values of continuous variables, an SE flag will be shown, while for graphs showing percentages, this will be the Wilson score asymptotic SE on the binomial proportions.

Calculated parameters will not be rounded in the derived datasets. The rounding will be done at the reporting level. Mean, median, 95% CI limits will be presented with one decimal more than data collected. Minimum and maximum will be reported with the same precision as data collected and SD and SE with two decimals more than data collected. Percentages will be tabulated with 1 decimal.

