## 8 ANALYSIS OF PHARMACOKINETICS

All analyses will be run on the PK population.

Drug concentration will be analyzed descriptively (n, arithmetic mean, SD and SE, median, minimum and maximum, 5% and 95% percentiles, CV% of arithmetic mean, geometric mean and geometric SD) by treatment group and timepoint.

Individual pharmacokinetic concentrations will be reported in  $\mu\text{g/mL}$ . Concentrations in  $\text{ng/mL}$  will be converted. Values BQL will be handled as detailed in section 4.3.2.

Pharmacokinetic concentrations and descriptive statistics will be reported to 3 significant digits for values up to, but not including 1000. Values equal to and above 1000 will be reported as the value without decimal signs. In case the actual sampling time deviates more than allowed per study protocol from the nominal time, these samples will not be included in the calculation of descriptive statistics.

A detailed list of tables and listings can be found in section 13.3 and section 15.4, respectively.

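### SAP 4.3.2 removes below-quantification concentrations from the PK summaries and no table counts them, so summary tables and mean plots read high whenever such values occur

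*SAP*

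**What the plan says.** SAP 4.3.2 sets a default for results beyond an assay limit: "Values below (above) the detection limit will be imputed by the value of the detection limit itself, unless indicated otherwise". PK concentrations are a stated exception. Individual results are reported as BQL, but for the mean, median, geometric mean, SD, CV%, minimum and maximum, "all BQL values will be treated as missing". There is a cap: "When the total number of BQL values exceeds 1/3 of the total number of values at that time point", the statistics are not computed and NC is printed.

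Percentiles are not in the list in 4.3.2, but SAP 4.3.1 adds them to the PK summary ("Descriptive statistics of PK concentrations will additionally include 5% and 95% percentiles"). SAP 8 lists them with the other statistics and sends the reader back: "Values BQL will be handled as detailed in section 4.3.2". I take the rule to cover them.

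Under SAP 4.3.1 the n shown for continuous variables counts non-missing observations, so a BQL result drops out of n as well. The descriptions of Table 14.2.6.1 and Figures 14.2.1.13.1 and 14.2.1.13.2 provide for no BQL count or percentage.

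The samples are troughs. Footnote K of the protocol's Schedule of Assessments states: "PK and immunogenicity samples will be taken predose".

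**The concern.** A BQL result is not missing. The sample was taken and assayed, and the concentration was found to be low. If such results are dropped from both the statistics and n, the table describes only subjects with quantifiable drug, under a heading that suggests the whole group. A reader cannot tell an assayed low result from a sample that was never drawn, and the printed minimum can never be BQL.

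Low troughs are of interest in this study. Protocol 1.1.1 names low serum levels, rapid clearance and immunogenicity among the reasons for losing response. Most doses may be self-administered at home, and Protocol 3.3.6 says: "Compliance will be further confirmed by bioanalytical assessment of ALX-0061 in serum samples". A trough summary that leaves out the lowest results answers a different question from the one a reader of a long-term extension will ask.

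**Working it through.** The plan states no figure on this point, so there is nothing to reproduce.

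**Inputs from the documents.** Deletion of BQL values and the one-third cap (SAP 4.3.2); the statistics reported (SAP 4.3.1 and 8); Week 0 as a PK time point (SAP 3.3); the treatment groups, five from C201 including former placebo and three from C202 (SAP 4.2.2); a pooled column in every table (SAP 4.2.3).

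**Inputs not in the documents.** The lower limit of quantification (LLOQ), the BQL share *f* and the between-subject variability for this regimen. I vary *f* from 5% to 33.3% and, where a distribution is needed, CV from 50% to 120%.

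**Step 1: quantiles, with no distributional assumption.** If the lowest fraction *f* is deleted, the *q*-quantile of what remains is the full-sample quantile *f* + *q*(1 − *f*). At *f* = 10% the reported median is 0.10 + 0.5 × 0.90 = 0.55, and the reported 5th percentile is 0.10 + 0.05 × 0.90 = 0.145.

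| BQL share | Reported median is the true | Reported 5th percentile is the true |
|---|---|---|
| 5% | 52.5th percentile | 9.8th percentile |
| 10% | 55th | 14.5th |
| 20% | 60th | 24th |
| 33.3% | 66.7th | 36.7th |

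**Step 2: size under a log-normal assumption.** Let s = √ln(1 + CV²) and let a be the standard normal *f*-quantile, so that the LLOQ sits at the *f*-quantile. Ratios of reported to true value are:

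- geometric mean: exp(s·φ(a)/(1 − *f*))
- median: exp(s·z(0.5 + *f*/2))
- arithmetic mean: Φ(s − a)/(1 − *f*)

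Worked case: for CV 50%, s = √ln 1.25 = 0.472. At *f* = 5%, φ(a)/(1 − *f*) = 0.1031/0.95 = 0.1086, and exp(0.472 × 0.1086) = 1.053.

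| BQL share | Arithmetic mean | Geometric mean | Median |
|---|---|---|---|
| 5% | 1.035–1.048 | 1.053–1.108 | 1.030–1.061 |
| 10% | 1.067–1.097 | 1.096–1.202 | 1.061–1.126 |
| 20% | 1.132–1.204 | 1.180–1.392 | 1.127–1.270 |
| 33.3% | 1.225–1.373 | 1.294–1.674 | 1.226–1.502 |

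Each range runs from CV 50% to CV 120%. At *f* = 0 every ratio is 1.

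**Step 3: Week 0.** Former-placebo subjects have had no ALX-0061 before the Week 0 predose sample and should be BQL. If the groups are of equal size, they are 1/5 = 20% of 'C201 all subjects' and 1/8 = 12.5% of 'All subjects'. Both shares are under one third. If no other results are BQL, the former-placebo subjects are dropped and the pooled means are still printed. Relative to counting them as zero, those means are 1/(1 − 0.20) = 1.25 and 1/(1 − 0.125) = 1.14 times as large.

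**The case against.** The strongest reply is that this may not matter much after Week 0. Dosing is every two weeks. Protocol 1.2.4.1 puts the half-life from linear clearance at about 15 days at high concentrations, though clearance is non-linear at lower ones. Study-visit doses up to Week 96 are given on site. The protocol also requires discontinuation after interrupted consecutive doses (3.2.3.2 and 3.4.1.2 word the threshold differently and need reconciling). Nothing in the documents shows that a large on-treatment BQL share is to be expected. This stands: the upper rows of the tables show what the rule permits and are not a forecast. The log-normal model also truncates a single population, whereas missed doses or antibody-driven clearance would produce a distinct subgroup. The quantile results hold either way; the mean ratios are illustrative.

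A reader might infer that low-exposure subjects are hidden altogether. The documents do not support that. Listing 16.2.4.1 gives every individual concentration, Figure 14.2.1.13.3 plots each subject's PK alongside antibody and response data, and Protocol 3.6.5 plans a separate population PK analysis. Nor is the compliance check defeated: SAP 12.2.1 measures compliance by doses received over doses expected, and the listing serves any check on an individual.

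A reader might also see a contradiction with the default of imputing the detection limit. There is none, because the default allows exceptions and PK is one. The one-third cap is a prespecified safeguard, but above it low exposure is not summarised at all.

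**Conclusion.** The point holds for the summary tables and mean plots. The upward direction follows from the rule itself and needs no assumption beyond at least one BQL result. It affects every location statistic and the minimum; the maximum is unchanged. The size depends on a BQL share that the documents do not give: nothing if there are none, a few percent on the median at 5% BQL, and substantial near the cap. A fixed claim of heavy inflation would go beyond the documents.

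Week 0 is the one place where BQL results are clearly to be expected. The 1.25 and 1.14 factors there rest on equal group sizes, on all former-placebo subjects being BQL, and on no one else being BQL. Only descriptive PK is concerned.

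**What to change.** Amend SAP 4.3.2 and the description of Table 14.2.6.1 as follows:

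- Report the number of samples assayed and the number and percentage BQL, per treatment group and visit, including where the other statistics are NC.
- Rank BQL results below the LLOQ for the minimum, median and percentiles, and print BQL where the statistic falls there. The median is then unbiased at any BQL share up to the one-third cap, and no substituted value is needed.
- Keep the arithmetic and geometric means under the present rule, but label them in the table and in the mean plots as computed on quantifiable values only.
- State whether the one-third share is counted within each treatment group or over all subjects at the visit. The present wording leaves this open.

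A sensitivity summary with a substituted value is optional. Substitution is a convention with its own bias: under the same log-normal assumptions, LLOQ/2 gives a geometric mean 0.88–0.99 times the true one. It should not be made a requirement.

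The cost is a few lines of SAP text and minor programming, with no new data.

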#### ***4.3.3 Handling of outliers***

There will be no outlier detection. All measured values will be included in the analyses.

### **4.4 Software and Validation Model**

SAS version 9.4 or higher will be used for programming.

Currently valid [REDACTED] standard operating procedures (SOPs) will be followed.

ACR20 response will be validated following Model C, other efficacy endpoints, general and safety parts following validation model B:

Model B: review of the output, source code and program log by an independent person (i.e., somebody different from the developer).

Model C: review of the output, source code and program log by an independent person, plus independent programming of the parameters indicated in this SAP.

## 5 GENERAL CHARACTERISTICS

All analyses on general characteristics will be run on the ITO population, unless specified otherwise.

### 5.1 Subject Disposition

Subject disposition will be presented descriptively for the all screened population. This includes the number and percentage of subjects in each of the analysis populations defined in section 4.1. Percentages will be calculated relative to the all screening population. A disposition summary by region and country and a summary by time point will be given for the ITO population. The number and percentage of subjects who completed the study and those who prematurely discontinued from the study will be summarized, along with the primary reasons for discontinuation.

A detailed list of tables and listings can be found in section 13.1 and section 15.1, respectively.

### 5.2 Protocol Deviations and Eligibility Criteria

A protocol deviation is any change, divergence, or departure from the study design or procedures defined in the protocol. Protocol deviations are considered as major if they concern criteria and disease characteristics that are critical to define the study population and criteria that determine or influence clinical endpoints or criteria that may cause immediate hazard to the subjects (impact on subjects' rights, safety or well-being) or increase the safety risk to subjects.

The list of (potentially) major protocol deviations will be reviewed by the sponsor and finalized prior to database lock. Detailed information can be found in the trial protocol deviation criteria list.

Major protocol deviations will be tabulated according to their category. The following categories are considered:

- Selection criteria not met
- Subject not withdrawn as per protocol
- Prohibited concomitant medication
- Treatment non-compliance
- Safety assessment deviation
- Efficacy assessment deviation
- Other

Additionally, major protocol deviations will be listed including categorization and description.

A detailed list of tables and listings can be found in section 13.1 and section 15.1, respectively.

### 5.3 Demographic and Other Baseline Characteristics

Demographic data and baseline disease characteristics will be summarized descriptively by treatment group and overall on the ITO population. The following demographic parameters and baseline disease characteristics will be included in the tables and/or listings:

#### Demographic parameters:

- Sex at birth (male, female)
- Women of childbearing potential (yes, no), only listed
- Age (years): the age at baseline of the parent trial is used.
- Age categories (<65 years, ≥65 years)
- Year of birth: only listed
- Date of signing the ICF: only listed
- Race (white, black or African American, Asian, American Indian or Alaska native, native Hawaiian or other Pacific Islander, other, not allowed to ask). Specification for Asian and other race will only be listed.
- Ethnicity (Hispanic or Latino, non-Hispanic or non-Latino, not allowed to ask)
- Geographic region (Latin America, Europe):
  - Latin America: Mexico
  - Europe: Spain, Germany, Poland, Belgium, Bulgaria, Republic of Moldova, Georgia, Hungary, Romania, Macedonia and Serbia
- Height (cm)
- Weight (kg)
- Weight categories ( $\leq$ 100 kg,  $>$ 100 kg;  $\leq$ median,  $>$ median)
- Body mass index BMI = (weight in kg) / (height in m) (kg/m^2)

Age, height, weight and their derived parameters will be extracted from the parent study. Previously calculated parameters will not be recalculated.

**Baseline disease characteristics:**

Please refer to the efficacy section 12.3 for detailed definitions of the parameters. Below baseline parameters will be extracted from the parent study and calculated parameters will not be recalculated.

- Swollen joint count (SJC66): number of swollen joints out of 66 assessed joints
- Tender joint count (TJC68): number of tender joints out of 68 assessed joints
- Swollen joint count (SJC28): number of swollen joints out of 28 assessed joints used for DAS28 calculation
- Tender joint count (TJC28): number of tender joints out of 28 assessed joints used for DAS28 calculation
- Tender joint count categories (<10, 10-20, >20)
- Swollen joint count categories (<7, 7-11, >11)
- CRP (mg/dL)
- CRP categories (<= upper limit of normal range [ULN], >ULN and <=1.2xULN, >1.2xULN and <=3xULN, >3xULN)
- ESR (mm/h)
- Physician's global assessment of the disease (VAS; 0-100 mm)
- Patient's global assessment of the disease (VAS; 0-100 mm)
- Patient's assessment of pain (VAS; 0-100 mm)
- HAQ-DI (0-3)
- SF-36 Physical component summary
- SF-36 Mental component summary
- Time since first RA symptoms (years)
- Time since RA diagnosis (years)
- ACR functional class at screening (of parent trial): class I / class II / class III / class IV
- Extra-articular symptom location: any of the following: skin, eyes, gastrointestinal, heart, lung, renal, nervous system, other
- Extra-articular symptoms: only listed
- Rheumatoid factor (RF) concentration (kIU/L)
- RF category (positive [>ULN], negative [<=ULN])
- Anti-CCP category (positive [>ULN], negative [<=ULN])
- Combined RF and anti-CCP category (double positive, double negative, mixed negative and positive)
- DAS28 Score (ESR)
- DAS28 Score (CRP)
- DAS28(ESR) and DAS28(CRP) categories (<=3.2, >3.2 and <=5.1, >5.1)
- Clinical Disease Activity Index (CDAI)
- Simplified Disease Activity Index (SDAI)
- MTX use (dose)

- Corticosteroid use (prednisone equivalent dose)
- Duration of morning stiffness (minutes)
- FACIT

A detailed list of tables and listings can be found in section 13.1 and section 15.1, respectively.

#### **5.4 Exposure to Study Medication and Treatment Compliance**

Extent of exposure will be analyzed descriptively by treatment group and overall based on the safety population. Note that only exposure during the OLE will be analyzed, so this will not reflect the total exposure of a subject to ALX-0061.

The following parameters will be summarized: total treatment duration, total number of study drug doses received, cumulative dose of study drug received, compliance and home administration. The derivation of these parameters can be found in section 12.2.1. A detailed list of tables and listings can be found in section 13.1 and section 15.1, respectively.

#### **5.5 Medical history**

Medical history was listed in the parent trials.

#### **5.6 Concomitant Therapies**

Any concomitant therapy taken during the study will be recorded in the eCRF, including ongoing concomitant therapies from the parent trial. Concomitant therapies are defined as therapies with a stop date on or after date of first dose of study drug in the C203 study. Therapies stopped before the study are not recorded. Analysis of prior medications is available in the parent trials.

All therapies are coded using the latest WHO-DRUG version. No anatomical therapeutic chemical classification system (ATC) selection is performed.

Concomitant therapies will be tabulated by generic term, for RA and non-RA medications separately, by treatment group and overall using the ITO population. Multiple records of the same generic term for the same subject will be counted only once. The table will therefore present subjects, not occurrences. The tables are sorted by decreasing frequency based on all subjects.

Systemic corticosteroids are selected as steroid RA-therapy with intravenous or intramuscular administration (not intra articular)

A detailed list of tables and listings can be found in section 13.1 and section 15.1, respectively.

